1.2 Schema

A schematic of the study design is provided in [Figure 1-1](#).

Figure 1-1: Study schematic

1.3 Schedule of activities

The schedule of activities is provided in [Table 1-1](#). For study participants entering MG0007, he/she must complete at least 6 visits and then complete the PEOT visit in MG0004, which serves as the Screening Visit for MG0007 and as the EOS for MG0004. If a study participant has completed the Treatment Period and is in the Observation Period of MG0004, he/she will then complete the EOS visit to serve as the Screening Visit for MG0007.

Table 1-1: Schedule of activities

	Week	Weeks 1-4		Weeks 5-8				Weeks 9-48 ^a		Weeks 49-51		Week 52	Week 60
	Visit ^b	1 (Screening /Baseline) ^c	2-4	5	6	7	8	1 st visit	2 nd , 3 rd , and 4 th visits	49	50 51	52 or PEOT	53 EOS
Assessments	Visit type	S	S	S	H	S	H	S	H	S	H	S	S
Written informed consent		X											
Verification of inclusion/exclusion criteria		X ^d											
Withdrawal criteria			X	X	X	X	X	X	X	X	X	X	
Medical history update		X		X				X		X		X	X
Concomitant medications and medical procedures		X	X	X	X	X	X	X	X	X	X	X	X
Body weight ^e		X						X				X	X
Vital signs		X	X	X	X	X	X	X	X	X	X	X	X
C-SSRS ^f		X											
Query for suicidality ^f			X	X		X		X		X		X	X
MGFA classification												X	X
QMG		X		X		X		X		X		X	X
MG-C Scale		X		X		X		X		X		X	X

Table 1-1: Schedule of activities

	Week	Weeks 1-4		Weeks 5-8				Weeks 9-48 ^a		Weeks 49-51		Week 52	Week 60
	Visit ^b	1 (Screening /Baseline) ^c	2-4	5	6	7	8	1 st visit	2 nd , 3 rd , and 4 th visits	49	50 51	52 or PEOT	53 EOS
Assessments	Visit type	S	S	S	H	S	H	S	H	S	H	S	S
MG-ADL		X		X		X		X		X		X	X
MG Symptoms PRO		X		X				X		X		X	X
EQ-5D-5L		X						X				X	
MGI ^g		X						X				X	
MGQoL15r		X						X		X		X	X
Full physical examination		X										X	X
Brief physical examination			X	X		X		X		X			
12-lead ECG		X		X				X ^h				X	X
Pregnancy test (urine) ⁱ		X						X		X		X	X
Hematology, serum chemistry, urinalysis		X	X			X		X		X		X	X
PTT and INR measurements		X										X	X
Serology testing for HIV, hepatitis B, and hepatitis C		X											
Anti-tetanus toxoid titer								X ^j					X
IGRA tuberculosis test												X	X
Tuberculosis signs and symptoms questionnaire		X		X				X ^k				X	X

Table 1-1: Schedule of activities

	Week	Weeks 1-4		Weeks 5-8				Weeks 9-48 ^a		Weeks 49-51		Week 52	Week 60
	Visit ^b	1 (Screening /Baseline) ^c	2-4	5	6	7	8	1 st visit	2 nd , 3 rd , and 4 th visits	49	50 51	52 or PEOT	53 EOS
Assessments	Visit type	S	S	S	H	S	H	S	H	S	H	S	S
Contact IRT		X	X	X	X	X	X	X	X	X	X	X	X
Study participants identification card assigned		X											
Recording of AEs		X	X	X	X	X	X	X	X	X	X	X	X
Blood sampling for PK ⁿ		X		X								X	
Blood sampling for ADA		X		X				X ^o				X	X
Blood sampling for IgG and IgG subclasses ^p		X	X	X		X		X		X		X	X
Blood sampling for IgA, IgM, IgE		X						X ^q				X ^r	X
Blood sampling for exploratory safety biomarker analysis ^s			X										
MG-specific autoantibodies		X		X				X ^o				X	X
Serum complement levels (C3,C4) and cytokines ^t			X					X					
Plasma complement levels (C3a and C5a) ^t			X					X					

Table 1-1: Schedule of activities

	Week	Weeks 1-4		Weeks 5-8				Weeks 9-48 ^a		Weeks 49-51		Week 52	Week 60
	Visit ^b	1 (Screening /Baseline) ^c	2-4	5	6	7	8	1 st visit	2 nd , 3 rd , and 4 th visits	49	50 51	52 or PEOT	53 EOS
Assessments	Visit type	S	S	S	H	S	H	S	H	S	H	S	S

ADA=anti-drug antibody; ADL=activities of daily living; AE=adverse event; AESM=adverse events of special monitoring; C-SSRS= Columbia Suicide Severity Rating Scale; ECG=electrocardiogram; EOS=End of Study; EQ-5D-5L=5-level European quality of life 5 dimension; GI=gastrointestinal; H=home visit; HIV=human immunodeficiency virus; Ig=immunoglobulin; IGRA=interferon gamma release assay; IMP=investigational medicinal product; INR=international normalized ratio; IRT=interactive response technology; MG=myasthenia gravis; MGII=myasthenia gravis impairment index; MG-ADL=myasthenia gravis-activities of daily living; MGFA=Myasthenia Gravis Foundation of America; MGQoL15r=revised 15-item myasthenia gravis quality of life questionnaire; PEOT=premature end of treatment; PK=pharmacokinetic(s); PRO=patient-reported outcome; PTT=partial thromboplastin time; QMG=quantitative myasthenia gravis test; S=site visit

^a From Weeks 9 to 48, the schedule will operate on recurring 4-week cycles wherein the first visit of each 4 weeks will be site visits and the subsequent 3 visits (2nd, 3rd, and 4th visits) will be home visits. Accordingly, Visits 9, 13, 17, 21, 25, 29, 33, 37, 41, and 45 will be site visits and the remaining visits will be home visits. At the discretion of the Investigator, home visits may be changed to site visits. Study participants may also choose to complete the visits at the site on the scheduled home visits.

^b Visit windows of ±2 days are allowed for all visits.

^c For any study participant who enrolls in MG0004, the final visit in MG0003 (Visit 14) or MGC003 (Visit 14) will serve as Visit 1 in MG0004. All activities should be completed at Visit 1 (±1 week).

^d For criteria pertaining to laboratory measures, the last available value from MG0003 or MGC003 will be used for evaluation of study participant eligibility, as long as the measurement was taken within the last 4 weeks (not older than 32 days) prior to MG0004 screening.

^e To be collected four times during the study: Screening/Baseline, 1 Week 25 (site visit), Week 52 (or PEOT), and EOS Visit.

^f A full Columbia-Suicide Severity Rating Scale (C-SSRS) assessment will be performed only when study participant has a positive response to Question 1 of the suicidal ideation query. If a study participant has active suicidal ideation as confirmed by the answer “Yes” to Question 4 or Question 5 of the C-SSRS assessments, the study participant will be excluded or withdrawn from the study and immediately referred to a mental healthcare professional. Complete C-SSRS will observe the “since last visit” version recorded at Visit 14 in MG0003 or MGC003.

^g MGII is optional for all study participants.

^h From Weeks 9 to 48, an ECG will be performed every 3 months (ie, Weeks 9, 21, 33, and 45).

ⁱ Urine pregnancy test will be performed using a dipstick test; a positive urine pregnancy test must be confirmed using a serum pregnancy test.

^j Every 6 months.

^k From Weeks 9 to 48, the tuberculosis questionnaire will be performed every 3 months (ie, Weeks 9, 21, 33, and 45).

- ^l Study participants must be observed at site postdose for at least 4 hours following the first 2 infusions, and then 2 hours thereafter for subsequent infusions until Week 7, where the participant can be observed for 1 hour at the Investigator's discretion.
- ^m No IMP administration will occur during the PEOT visit for study participants who withdraw from the study or discontinue IMP.
- ⁿ PK samples should be taken predose for all study participants.
- ^o From Weeks 9 to 48, ADA- and MG-specific autoantibodies will be measured every 3 months (ie, Weeks 9, 21, 33, and 45).
- ^p Total IgG will be assessed at all scheduled onsite visits; IgG subclasses will be assessed at Visit 1 and every 3 months thereafter.
- ^q From Weeks 9 to 48, blood sampling for IgA, IgE and IgM will be measured every 3 months (ie, Weeks 9, 21, 33, and 45).
- ^r To be performed only in the event of a PEOT Visit.
- ^s Baseline from MG0003 and MGC003 will serve as Baseline in MG0004. Additional exploratory safety samples must be collected 4 hours postevent or as soon as possible before the next IMP in case of AESM of serious or severe headache or AESM of GI disorders as described in Section 8.9.
- ^t Baseline from MG0003 and MGC003 will serve as Baseline in MG0004. Additional samples may be collected 2 hours and 4 hours postevent in case of severe headache, infusion reaction, or hypersensitivity reaction at Visits 5, 7, 1st visit (of the 4-week cycle from Weeks 9-48) and Visit 49.

PUBLIC COPY
This document cannot be used to support any marketing authorization application and any extensions or variations thereof.

2 INTRODUCTION

Rozanolixizumab is a humanized IgG4 monoclonal antibody that is being developed as an inhibitor of the activity of the FcRn for IgG.

By blocking the activity of FcRn, rozanolixizumab accelerates the catabolism of IgG antibodies, including IgG autoantibodies. The aim is to reduce the concentration of pathogenic IgG in study participants with autoimmune diseases mediated by the action of IgG autoantibodies.

The FcRn recycles IgG and albumin and transports it bidirectionally across epithelial barriers. Recent studies have shown that FcRn rescues both IgG and albumin from intracellular lysosomal degradation by recycling it from the sorting endosome to the cell surface (Roopenian and Akilesh, 2007). FcRn may also mediate transcytosis of IgG to facilitate its distribution within tissues. Rozanolixizumab has been specifically designed to block IgG binding to FcRn without blocking the binding and recycling of albumin.

Rozanolixizumab binds with high affinity to FcRn at both neutral and acidic pH. Immunoglobulin G that is constitutively taken up by pinocytosis into cells fails to bind to FcRn, even at the acidic pH found in the endosome. It is therefore not recycled and is trafficked to the lysosomes for degradation.

Production of pathogenic IgG autoantibodies is the major pathophysiology leading to a number of autoimmune diseases, which include MG, pemphigus vulgaris (PV), immune thrombocytopenia (ITP), Goodpasture's syndrome, neuromyelitis optica, Guillain-Barré Syndrome (GBS), and chronic inflammatory demyelinating polyradiculoneuropathy.

As individual disease entities, IgG autoantibody-mediated conditions are relatively rare. Treatment of these disorders remains a difficult clinical problem, requiring in many of these conditions the long-term use of corticosteroids alone or combined with cytotoxic agents. These therapeutic approaches are not effective in all study participants and conditions and have broad immunosuppressive effects causing considerable toxicity and treatment-related morbidity.

Treatments aimed at reducing the quantity of circulating IgG autoantibodies, including plasmapheresis, immunoadsorption, or high dose IVIg, are being used for primary and secondary therapy of autoimmune disease, particularly where corticosteroid based immune suppression is not or no longer effective (eg, ITP, MG, GBS, PV). The therapeutic approach of these treatments is thought in part to be based on lowering levels of pathogenic autoantibodies, which represents rational and effective treatment modalities of autoimmune diseases.

Therefore, specific removal of the IgG autoantibodies by FcRn blockade may provide an effective therapeutic option for IgG autoantibody-mediated autoimmune disorders.

More detailed information regarding the nonclinical and clinical development programs for rozanolixizumab, including all completed and ongoing studies, can be found in the latest version of the Investigator's Brochure (IB).

2.1 Study rationale

Myasthenia gravis is a serious, debilitating, sometimes life-threatening condition that is associated with numerous symptoms, including muscular weakness and fatigue. The major pathophysiology leading to MG is the abnormal production of IgG autoantibodies directed toward nicotinic AChR, or MuSK protein. Several commonly prescribed treatments act, at least

in part, by reducing the quantity of such circulating IgG autoantibodies. While the standard of care for MG involves the utilization of a variety of therapeutic agents including cholinesterase inhibitors, immunomodulators, corticosteroids, biologics interfering with IgG turnover, high-dose IVIg, plasmapheresis, or immunoabsorption, there remains a need for a safe and effective treatment devoid of significant side effects to conveniently treat study participants with MG.

By blocking the activity of FcRn, rozanolixizumab accelerates the catabolism of antibodies and reduces the concentration of pathogenic IgG in MG study participants, thus offering a safe, effective, and convenient alternative to existing treatments. A Phase 3 study (MG0003) is underway to establish the safety and efficacy of rozanolixizumab in study participants with generalized MG who experience moderate-to-severe symptoms.

This open-label extension study (MG0004) will evaluate the long-term safety, tolerability, and efficacy of rozanolixizumab.

2.2 Background

Rozanolixizumab is a humanized anti-FcRn monoclonal antibody that has been specifically designed to inhibit IgG binding to FcRn without inhibiting albumin binding to FcRn.

Rozanolixizumab is being developed as an inhibitor of FcRn activity with the aim to reduce the concentration of pathogenic IgG in study participants with IgG autoantibody-mediated diseases.

To date, rozanolixizumab has been administered to human study participants in 6 completed or ongoing clinical studies: UP0018, MG0002, MG0003, TP0001, CIDP01, and UP0060. UP0018 is a completed first-in-human study, MG0002 is a completed Phase 2 study in study participants with generalized MG, and TP0001 is a completed Phase 2 study in study participants with primary ITP, and UP0060 is an ongoing Phase 1 study comparing the safety, tolerability, pharmacokinetics (PK), and pharmacodynamics (PD) of rozanolixizumab in Chinese, Japanese and Caucasian healthy volunteers.

In MG0002, clinically relevant improvements in day-to-day functioning, as measured by change from Baseline to Day 29 in myasthenia gravis-activities of daily living (MG-ADL) (secondary endpoint), were observed following treatment with rozanolixizumab [REDACTED] compared with placebo (p=0.036). Numerical differences numerical in favor of rozanolixizumab [REDACTED] compared with placebo were observed in reductions from Baseline in quantitative myasthenia gravis (QMG) (p=0.221) and MG-C score (p=0.089). Overall, repeated administrations of rozanolixizumab at dose levels of [REDACTED] SC have been generally well tolerated, with an acceptable safety profile. No new safety concerns were identified. The treatment-emergent adverse event (TEAE) profile was similar between rozanolixizumab and placebo except for headaches where increased frequency and severity was observed in the rozanolixizumab study participants.

Final data from the proof-of-concept ITP study TP0001 demonstrated that rozanolixizumab was tolerated with an acceptable safety profile after multiple [REDACTED] and single [REDACTED] doses.

MG0003 is a Phase 3, randomized, double-blind, placebo-controlled study to evaluate the efficacy and safety of 2 doses of rozanolixizumab (equivalent to approximately [REDACTED]

██████████) in study participants with generalized MG who experience moderate to severe symptoms and are being considered for treatment with IVIg or PEX.

This study (MG0004) is an open-label extension study for the global lead-in study MG0003 and China specific lead-in study, MGC003 (this study will mirror the study design of MG0003). MG0004 will evaluate the long-term safety, tolerability, and efficacy of rozanolixizumab in study participants with generalized MG. Study participants in MG0004 will be randomized to receive 1 of 2 doses of rozanolixizumab (equivalent to approximately ██████████ respectively) over a 52-week Treatment Period.

2.3 Benefit/Risk assessment

Generalized MG is a rare, debilitating, chronic autoimmune disease driven by, in large part, IgG autoantibodies that target neuromuscular junctions (NMJs). Most current treatment approaches are not targeted treatments to the specific underlying pathology of IgG autoantibody formation, but rather they produce a broad cascade of immune suppression, which results in undesirable side effects such as those seen with high-dose chronic steroid use. Many treatments of choice often require invasive, expensive, and time-consuming inpatient procedures such as PEX, or intravenous (IV) administration of immunoglobulins at a healthcare facility.

Rozanolixizumab represents an innovative, SC anti-FcRn monoclonal antibody that may provide a novel and specific therapeutic approach for the treatment of study participants with MG. Data show that rozanolixizumab markedly lowers serum IgG and IgG autoantibody levels in study participants with generalized MG. The completed Phase 2 study MG0002 established supportive evidence of efficacy for the treatment of MG, achieving significant and clinically meaningful improvements to Day 29 in MG-ADL with rozanolixizumab ██████████ compared with placebo ($p=0.036$). Repeated administrations of rozanolixizumab were generally well tolerated, with an acceptable safety profile and in line with SC dosing in the Phase 1 program and the safety profile observed in TP0001.

The potential risks associated with SC administration of rozanolixizumab are gastrointestinal (GI) disturbances, headaches, infusion/hypersensitivity reactions, infections, potential effects on immunizations, effects on the kidney, and metabolic effect of FcRn on albumin. These risks can be mitigated by careful monitoring, exclusion of at-risk study participants, and appropriate protocol withdrawal and stopping criteria. Additionally, protocol guidance for management of GI disturbances, severe headaches, and infusions/hypersensitivity reactions is also provided as well as expedited reporting requirements of adverse events of special monitoring (AESMs).

More detailed information about the known and expected benefits and risks and reasonably expected adverse events (AEs) of rozanolixizumab may be found in the IB.

3 OBJECTIVES AND ENDPOINTS

Objectives	Endpoints
Primary	

To evaluate the long-term safety and tolerability of rozanolixizumab in study participants with generalized MG
	
The primary safety endpoints are:
 
 • Occurrence of TEAEs • Occurrence of TEAEs leading to permanent withdrawal of study medication 
The other safety endpoints are:
 
 • Occurrence of AESMs • Vital sign values and changes from Baseline (systolic and diastolic blood pressure and pulse rate) • 12-lead ECG values and change from Baseline at each scheduled assessment • Clinical laboratory findings (hematology, biochemistry, and urinalysis)
Secondary	

To evaluate the long-term efficacy of rozanolixizumab in study participants with generalized MG
	
The secondary efficacy endpoints are:
 
 • Change from Baseline in MG-ADL at each scheduled assessment during Treatment and Observation Periods • Change from Baseline in MG-C score at each scheduled assessment during Treatment and Observation Periods • Change from Baseline in QMG at each scheduled assessment during Treatment and Observation Periods • Use of rescue medication (IVIg or PEX) 
The other efficacy endpoints are:
 
 • Change from Baseline in MGII scores at each scheduled assessment during Treatment and Observation Periods • Change from Baseline in MGII ocular subscores at each scheduled assessment during Treatment and Observation Periods • Change from Baseline in MGII generalized domain subscores at each scheduled assessment during Treatment and Observation Periods

	
• Change from Baseline in the MG Symptoms PRO ‘Muscle Weakness Fatigability’ score at each scheduled assessment during Treatment and Observation Periods• Change from Baseline in the MG Symptoms PRO ‘Physical Fatigue’ score at each scheduled assessment during Treatment and Observation Periods• Change from Baseline in the MG Symptoms PRO ‘Bulbar symptoms’ score at each scheduled assessment during Treatment and Observation Periods• Change from Baseline in the MG Symptoms PRO ‘Respiratory symptoms’ score at each scheduled assessment during Treatment and Observation Periods• Change from Baseline in the MG Symptoms PRO ‘Ocular symptoms’ score at each scheduled assessment during Treatment and Observation Periods• Change from Baseline in the MG Symptoms PRO multicomponent total score, at each scheduled assessment during Treatment and Observation Periods• Change from Baseline in the enhanced MG Symptoms PRO total score, at each scheduled assessment during Treatment and Observation Periods• Change from Baseline in MGQoL15r at each scheduled assessment during Treatment and Observation Periods• Change from Baseline in EQ-5D-5L scores at each scheduled assessment during Treatment and Observation Periods 
For study participants who require rescue treatment during the Observation Period of MG0003 and subsequently enter MG0004, the following endpoints will be assessed:
 
• QMG responder rate (≥ 3.0 point improvement from Baseline) at each scheduled assessment during the first 6 weeks of the Treatment Period• MG-C responder rate (≥ 5.0 point improvement from Baseline) at each
--	--

	
scheduled assessment during the first 6 weeks of the Treatment Period
 
 • MG-ADL responder rate (≥ 2.0 point improvement from Baseline) at each scheduled assessment during the first 6 weeks of the Treatment Period
Other	
To assess the reduction in use of steroids in study participants receiving rozanolixizumab	
 • AUC of the oral steroid dose over time
To assess the plasma concentrations of rozanolixizumab administered by SC infusion	
 • Plasma concentration of rozanolixizumab at each scheduled assessment during the Treatment and Observation Periods
To assess the pharmacodynamic effects of rozanolixizumab as measured by IgG levels, IgG subclasses, and MG-specific autoantibodies levels	
 • Change from baseline in total IgG and IgG subclasses autoantibodies at each scheduled visit • Change from baseline in MG-specific autoantibodies at each scheduled visit
To evaluate the incidence and emergence of ADAs with respect to immunogenicity, PK, and pharmacodynamics	
 • ADAs at each scheduled assessment during the Treatment Period and Observation Periods
To assess the effect of rozanolixizumab on biomarkers including IgM, IgA, and IgE, serum and plasma complement levels, and serum cytokines	
 • Change from Baseline in serum complement levels (C3 and C4) and plasma complement levels (C3a and C5a) at each scheduled assessment during Treatment Period^a • Change from Baseline in serum cytokines at each scheduled assessment during Treatment and Observation Periods^a • Change from Baseline in serum immunoglobulin concentrations (total IgA, IgE, and IgM) at each scheduled assessment during Treatment and Observation Periods
To assess the effect of rozanolixizumab on tetanus IgG antibodies	
 • Change from Baseline in anti-tetanus toxoid serum titers at each scheduled assessment during Treatment and Observation Period

ADA=anti-drug antibody; ADL=activities of daily living; AESM=adverse event of special monitoring; ECG=electrocardiogram; Ig=immunoglobulin; IVIg=intravenous infusion of immunoglobulin G; MG=myasthenia gravis; MG-ADL=myasthenia gravis-activities of daily living; MGII=myasthenia gravis impairment index; MGQoL15r=revised 15-item myasthenia gravis quality of life questionnaire; PEX=plasma exchange; PK=pharmacokinetic; PRO=patient-reported outcome; QMG=quantitative myasthenia gravis test; SC=subcutaneous(ly); TEAE=treatment-emergent adverse event

^a To be performed for study participants with severe and/or serious headache and/or infusion reaction or hypersensitivity reaction. Other exploratory safety biomarkers may be assessed.

Estimands

The aim of MG0004 is to compare safety (primarily) of long-term treatment of 2 dose levels of rozanolixizumab. Rescue medication is allowed and is expected to be temporary; dose switching (up or down) is also allowed. Using a treatment policy estimand is considered the only viable option to deal with this complexity. Indeed, a hypothetical estimand that appropriately accounted for treatment switching in this study, differing lengths of treatment in MG0004, and differing exposure to rescue medications in both studies would be very assumption-rich. This estimand will be based on the Safety Set (SS).

For all variables, the population is the study participants meeting the protocol-specified inclusion/exclusion criteria. The main intercurrent events are the use of rescue medication during the course of the study, withdrawal due to TEAEs and treatment switching.

All safety variables, biomarkers, and anti-drug antibody (ADA) results will be summarized for the SS classified by first treatment dose received [REDACTED] in this study (ie, before any switching occurs), both with and without subdivision by treatment dose received in MG0003 (placebo or [REDACTED]).

Efficacy variables will be summarized using a ‘treatment policy’ approach as follows:

- Participant-level outcome: The given variable and time point being summarized (eg, value of MG-ADL at Week 5).
- Population-level summary measure: For categorical variables, unadjusted proportions by first treatment received and, for continuous variables, unadjusted means by first treatment received.

Missing values will not be imputed.

Further details will be provided in the Statistical Analysis Plan (SAP).

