7.2 Participant discontinuation/withdrawal from the study

Study participants are free to withdraw from the study at any time, without prejudice to their continued care.

A study participant may also be withdrawn at any time at the discretion of the Investigator for safety, behavioral, compliance, or administrative reasons.

If the participant withdraws consent for disclosure of future information, the Sponsor may retain and continue to use any data collected before such a withdrawal of consent.

If a participant withdraws from the study, he/she may request destruction of any samples taken and not tested, and the Investigator must document this in the site study records.

See the Schedule of Activities (Section 1.3) for data to be collected at the time of study discontinuation and follow-up and for any further evaluations that need to be completed.

Study participants **must** be withdrawn from the study if any of the following events occur:

1. Study participant withdraws his or her consent.
2. The Sponsor or a regulatory agency requests withdrawal of the study participant.
3. Study participant becomes pregnant during the study, as confirmed by a positive pregnancy test.
4. Study participant has active suicidal ideation as indicated by a positive response (Yes) to either Question 4 or Question 5 of the "Since Last Visit" version of the C-SSRS. The study participant should be referred immediately to a mental healthcare professional.

Study participants who withdraw from the study or discontinue study medication during the Treatment Period should complete the assessments outlined for premature end of treatment (PEOT) visit and enter the Observation Period.

Study participants who withdraw for any reason will not be eligible to participate in the managed access program.

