9.6 Handling of dropouts or missing data

All imputation of missing or partial dates for safety assessments will be detailed in the SAP. Efficacy data will be summarized only and no imputation will be performed..

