3.2.2 Study periods

The maximum duration of the study per participant will be approximately 60 weeks, consisting of the following 2 periods:

- Treatment Period: 52 weeks
- Observation Period: 8 weeks

The end of the study is defined as the date of the last visit of the last participant in the study.

The following definitions for starting and entering the study periods will be applied:

- **Treatment Period** starts with the first day of IMP in MG0004 and ends after Week 52 or PEOT assessments. All participants in the Safety Set will be considered to have started the Treatment Period. A participant is considered to have completed the Treatment Period if assessments from Treatment Period Week 52 are completed.
- **Observation Period** starts with one day after the end of the Treatment Period and ends after the final assessments at the End of Study (EOS) visit. Participants with assessment on any Observation Period day are considered to have started the Observation Period. Participants who complete the assessments at the EOS visit will be considered to have completed the

Observation Period. Participants who have a completed status in the study termination case report form (CRF) are considered to have completed the Treatment and Observation Period.

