3.2.3 Mapping of assessments performed at Premature End of Treatment Visit

PEOT assessments will be assigned to the next scheduled site visit (following the last scheduled visit that the participant completed prior to PEOT) where each assessment is evaluated as per protocol. This approach means that there is a chance that PEOT data will be mapped to different visits according to the schedule of assessments.

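### The treatment-policy label does not fit permanent withdrawal: after PEOT, the Treatment Period efficacy means are observed-case means

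*Protocol*

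**What the plan says.** The Estimands text in Protocol Section 3 gives its reason for the strategy: "Using a treatment policy estimand is considered the only viable option to deal with this complexity". It rests on the Safety Set and lists the events in view: "The main intercurrent events are the use of rescue medication during the course of the study, withdrawal due to TEAEs and treatment switching". For efficacy, the participant-level outcome is the value of a variable at a time point, and the summary is, "for continuous variables, unadjusted means by first treatment received". On gaps it says "Missing values will not be imputed", and Protocol 9.6 repeats this for efficacy: "Efficacy data will be summarized only and no imputation will be performed".

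What happens after stopping is set elsewhere. Under Protocol 7.2, participants who withdraw or stop drug in the Treatment Period "should complete the assessments outlined for premature end of treatment (PEOT) visit and enter the Observation Period". SAP 3.2.2 agrees: the Treatment Period "starts with the first day of IMP in MG0004 and ends after Week 52 or PEOT assessments". SAP 3.2.3 keeps one further value in the by-visit tables: "PEOT assessments will be assigned to the next scheduled site visit". In Table 1-1 the only Observation Period visit is EOS.

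SAP 9.1.1 to 9.1.3 summarise the three scores by first dose received and scheduled visit. SAP 4.7 plans no sensitivity analysis for efficacy.

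**The concern.** Under treatment policy, the value at a time point counts whether or not the intercurrent event has happened. Applied to withdrawal, the strategy needs MG-ADL, MG-C and QMG values at the scheduled visits after drug is stopped. The schedule does not provide them, and nothing stands in for them.

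The event is foreseeable. Protocol 7.1.3 lists several adverse events that require permanent discontinuation, and Appendix 20 calls headache the most commonly reported adverse drug reaction.

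The three continuous secondary endpoints could then be read at Week 52 as covering everyone who started, when they cover a remaining subset. If those who left were doing differently from those who stayed, the label would hide that difference.

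**Working it through.** **Step 1. Each event against the data that follow it.**

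| Event | Treatment Period data afterwards | What the by-visit mean delivers |
|---|---|---|
| Rescue (named) | Visits continue during the drug pause (Protocol 6.5.3) | Treatment policy |
| Dose switch (named) | Visits continue; participant stays under first dose (SAP 3.6, 9) | Treatment policy |
| Permanent withdrawal (named when due to TEAEs) | One PEOT value at the next visit, then none | Observed case |
| Transfer to MG0007 from the Treatment Period (not named) | One PEOT value, which also closes MG0004 (Protocol 4.1) | Observed case |

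**Step 2. Visits lost.** In Table 1-1, MG-ADL, MG-C and QMG share one schedule. The post-baseline Treatment Period visits are 5 and 7, then 9, 13, 17, 21, 25, 29, 33, 37, 41 and 45, then 49 and 52: 2 + 10 + 2 = 14. With PEOT assigned as SAP 3.2.3 directs:

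| Last completed visit | Values before PEOT | PEOT goes to | Visits without a value |
|---|---|---|---|
| 4 | 0 | 5 | 14 - 0 - 1 = 13 |
| 6 | 1 | 7 | 14 - 1 - 1 = 12 |
| 10 | 3 | 13 | 14 - 3 - 1 = 10 |
| 26 | 7 | 29 | 14 - 7 - 1 = 6 |
| 44 | 11 | 45 | 14 - 11 - 1 = 2 |

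The row for Visit 6 is also the case of a transfer to MG0007 at the 6-visit minimum. EOS values do not fill these gaps: apart from PEOT, SAP 3.2.1 applies no visit windows, so an EOS value stays under EOS.

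**Step 3. What the gap can do to a mean.** Let d be the share with no value at a visit, O the mean change in those observed, M the mean change in those missing, and D = M - O. Higher scores are worse, so D > 0 means that the missing participants did worse.

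- Treatment-policy mean = (1 - d) x O + d x M = O + d x D.
- Observed-case mean minus treatment-policy mean = -d x D.

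The documents give neither d nor D, and there is no planned figure to reproduce. Taking d from 5% to 30% and an absolute D from 1 to 4 MG-ADL points, all assumed:

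- Smallest: 0.05 x 1 = 0.05 points.
- Middle: 0.20 x 3 = 0.6 points.
- Largest: 0.30 x 4 = 1.2 points.
- Between dose arms, with 10% and 25% missing and the same D: (0.25 - 0.10) x D = 0.15 to 0.6 points.

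The sign follows D. If those who left were doing better, the observed mean would understate improvement.

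**The case against.** The plan is open about its method. The Estimands text defines its approach as unadjusted means without imputation, so the observed-case basis is visible there. SAP 3.1 shows n in every continuous summary. SAP 5.1 reports discontinuation reasons, including transition to MG0007, and a count of participants by visit. This stands, and it limits how far a careful reader could be misled. But counts show how many left, not how they were doing, and the named strategy remains unsupported for one of its three named events.

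The argument for treatment policy also rests mainly on rescue, dose switching and differing treatment lengths, in a study that is primarily about safety. That is a fair reading. What is missing is a workable efficacy handling of withdrawal.

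A reader might infer that the means describe only participants on drug. They do not. Participants paused for rescue, low IgG, infection or COVID-19 keep attending (Protocol 6.5.3, 7.1.4), each PEOT value is carried to one further visit, and EOS values off drug are summarised.

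A reader might also infer that nothing at all is imputed. The SAP fills missing items within several scales (13.1, 13.3 to 13.6). SAP 9.2.5 to 9.2.7 mention NRI for responder rates, although SAP 4.2.1 contains no such rule and observed responders are what is summarised. None of this fills a missing visit in the three continuous scores.

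Finally, Protocol 7.1.1 and 7.1.2 tell participants who meet a stopping criterion to follow the visit schedule, which could mean continued Treatment Period visits. Neither says which schedule applies, and 7.1.2 itself moves the participant into the Observation Period.

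**Conclusion.** The point holds for permanent withdrawal. Beyond the visit that receives the PEOT value, the Treatment Period means of MG-ADL, MG-C and QMG are observed-case means among participants who have not permanently stopped. They are not treatment-policy results for that event. Transfer to MG0007 has the same effect without being named. For rescue and dose switching the stated strategy works.

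It would be tempting to conclude that Week 52 improvement is overstated by some tenths of a point or more. The documents do not support that: the rates and gaps in Step 3 are assumptions, and leaving because of a TEAE is not the same as leaving for lack of effect. The 2-point MG-ADL change in Protocol 8.1.3.1 marks clinical improvement and is not a yardstick for bias in a group mean. Efficacy is secondary, descriptive and untested (SAP 4.1, 4.6, 9), so no error rate or decision rule is affected. What changes is what the by-visit means can be said to show.

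**What to change.** In Protocol Section 3 and SAP Section 9:

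- Keep treatment policy for rescue and dose switching.
- State that, for permanent withdrawal and for transfer to MG0007, the by-visit efficacy summaries are observed-case.
- Label those tables *participants not permanently discontinued at the visit, plus mapped PEOT values*. A label such as *on treatment at the visit* would be wrong, because paused participants and PEOT values are included.
- Add one descriptive summary per secondary score: change from Baseline at the last Treatment Period assessment (Week 52 or PEOT) in the Safety Set, split by completed, withdrawn and transferred to MG0007, with time on study shown.
- Reconcile the visit-schedule sentences in Protocol 7.1.1 and 7.1.2 with 7.2.

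The cost is wording plus one summary per score from data already collected. The efficacy claim becomes narrower, and the added summary mixes treatment durations, which is why time on study belongs beside it. It does not recover the values that were never collected.
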